2. LIST OF ABBREVIATIONS

Term	Definition / description
ADPC	Proper name of the analysis dataset containing PK concentrations per time-point or per time-interval
ADPP	Proper name of the analysis dataset containing calculated PK parameters
ADS	Analysis dataset
AE	Adverse Event
AESI	Adverse event of special interest
AUC _{0-τ}	area under the concentration-time curve of the analyte over the time interval from τ
AUC _{0-tz}	Area under the concentration-time curve of the analyte in plasma over the time interval from 0 to the last quantifiable data point
BI	Boehringer Ingelheim
BLQ	Below the lower limit of quantification
BRPM	Blinded Report Planning Meeting
CARE	Clinical data analysis and reporting environment
C _{max}	Maximum measured concentration of the analyte in plasma
C _{max,ss}	maximum measured concentration of the analyte at steady state
CRF	Case Report Form
CTP	Clinical Trial Protocol
CTR	Clinical Trial Report
CV	Arithmetic coefficient of variation
ECG	Electrocardiogram
f _{faeces, 0-t2}	fraction of [¹⁴ C]-radioactivity excreted in faeces as percentage of the administered oral dose over the time interval from 0 to the last quantifiable time point
f _{urine, 0-t2}	fraction of [¹⁴ C]-radioactivity excreted in urine as percentage of the administered oral dose over the time interval from 0 to the last quantifiable time point
gCV	Geometric coefficient of variation
gMean	Geometric mean
ICH	International Conference On Harmonisation
MedDRA	Medical Dictionary For Regulatory Activities
NOA	Not analysed

Term	Definition / description
NOR	No valid result
NOS	No sample available
PK	Pharmacokinetics
PKS	Pharmacokinetic parameter analysis set
PSTAT	Project Statistician
PT	Preferred Term
PV	Protocol Violation
Q1	Lower Quartile
Q3	Upper Quartile
RAGe	Report appendix generator
SD	Standard Deviation
SDL	Subject data listing
SOC	System Organ Class
TS	Treated Set
TSAP	Trial Statistical Analysis Plan
ULN	Upper limit of normal range

3. INTRODUCTION

As per ICH E9 (1), the purpose of this document is to provide a more technical and detailed elaboration of the principal features of the analysis described in the revised CTP, and to include detailed procedures for executing the statistical analysis of the primary and secondary variables and other data.

This TSAP assumes familiarity with the CTP and its amendments. In particular, the TSAP is based on the planned analysis specification as written in CTP Section 7 "Statistical Methods and Determination of Sample Size". Therefore, TSAP readers may consult the CTP for more background information on the study, e.g., on study objectives, study design and population, treatments, definition of measurements and variables, planning of sample size, randomisation.

CRF data entered by the site will be stored in a trial database within the Oracle Clinical™ system. Electronically transferred data will be stored in CDR.

The statistical analyses will be performed within the validated working environment CARE, including SAS™ (current Version 9.4, by SAS Institute Inc., Cary, NC, USA), and a number of SAS™-based tools (e.g., macros for the analyses of AE data or laboratory data; Report Appendix Generator system (RAGe) for compilation/formatting of the CTR appendices).

PK parameters will be calculated using Phoenix WinNonlin™ software (version 6.3, Certara USA Inc., Princeton, NJ, USA).

4. CHANGES IN THE PLANNED ANALYSIS OF THE STUDY

All analyses described in this TSAP are in accordance with the statistical methods described in the revised CTP.

5. ENDPOINTS

5.1 PRIMARY ENDPOINTS

Primary endpoints are PK endpoints as defined in Section 5.5.1.1 of the CTP:

- $f_{urine, 0-t_2}$ (fraction of [^{14}C]-radioactivity excreted in urine as percentage of the administered oral dose over the time interval from 0 to the last quantifiable time point)
- $f_{faeces, 0-t_2}$ (fraction of [^{14}C]-radioactivity excreted in faeces as percentage of the administered oral dose over the time interval from 0 to the last quantifiable time point)

CTP: Timeframe: The timeframe for determination of these endpoints depends on discharge of radioactivity from each individual subject and is predicted to vary between 2-7 weeks after drug administration.

5.2 SECONDARY ENDPOINTS

5.2.1 Key secondary endpoints

Not applicable.

5.2.2 Secondary endpoints

Secondary PK endpoints will be defined as in Section 5.5.1.2 of the CTP.

Secondary endpoints in the single dose treatment group are C_{max} and AUC_{0-tz} of total radioactivity and C_{max} and AUC_{0-tz} of BI 1467335 in plasma.

Secondary endpoints in the multiple doses treatment group are C_{max} and AUC_{0-tz} of total radioactivity and $C_{max,ss}$ and $AUC_{0-\tau}$ of BI 1467335 in plasma.

5.3.2 Safety parameters

Further safety parameters of interest will be used as defined in Section 5.2.1 of the CTP:

CTP:

- AEs (including clinically relevant findings from the physical examination)
- Safety laboratory tests
- 12-lead ECG
- Vital signs (blood pressure, pulse rate)

6. GENERAL ANALYSIS DEFINITIONS

6.1 TREATMENT(S)

For basic study information on treatments to be administered, assignment of treatment groups, and selection of doses, cf. Section 4 of the CTP.

Subjects were planned to be treated either with

- a single dose of [¹⁴C]BI 1467335 (10 mg BI 1467335 calculated as free base) or
- multiple dose of 10 mg BI 1467335 and a single dose of [¹⁴C] BI 1467335 (10 mg BI 1467335 calculated as free base) on Day 28

Subjects in the multiple doses treatment group will receive unlabelled 10 mg BI 1467335 as film-coated tablet once daily from Day 1 to Day 27. In the morning of Day 28, following an overnight fast of at least 10 h, the subjects will receive one single oral dose of the radiolabelled trial drug. Treatment with nonradiolabelled compound (film-coated tablets) will continue from Day 29 up to Day 40, but may be stopped earlier in case release criteria have been met, cf. Section 3.1 of the CTP.

For statistical analysis of AEs, safety laboratory data and vital signs, the following analysis phases are defined for each subject:

Table 6.1: 1 Flow chart of analysis phases for statistical analyses of AEs, safety laboratory data and vital signs

Study analysis phase	Label	Start (inclusive)	End (exclusive)
Screening	Screening	Date of informed consent	Date/time of administration of study drug
On-treatment	10 mg BI SD, or 10 mg BI MD, respectively	Date/time of administration of study drug	0:00 AM on day after subject's trial termination date

Appendix 16.1.13.1.8.1 and Appendix 16.1.13.1.8.2 AE displays will present results for the on-treatment phase only. CTR Section 15 will present results for the screening and on-treatment phase.

In CTR Section 15 AE tables (but not in Appendix 16.1.13.1.8.1 and Appendix 16.1.13.1.8.2 AE tables), the following total will be provided in addition:

- "**Total on-trt BI**", defined as the total over all on-treatment phases involving BI 1467335
- "**Total**", defined as the total over all study phases (incl. screening and on-treatment).

More details on the technical implementation of these analyses are provided in the ADS Plan of this TSAP.

6.2 IMPORTANT PROTOCOL VIOLATIONS

Consistency check listings (for identification of violations of time windows) and a list of protocol deviations (e.g. deviations in drug administration) will be provided to be discussed at the RPM/DBLM. At this meeting, each protocol deviation must be assessed to determine whether it is an IPV. For definition of IPV, and for the process of identification of these, refer to the BI reference document "Protocol Violation Handling Definitions" (2).

Table 6.2: 1 Important protocol violations

Category / Code	Description
A	Entrance criteria not met
A1	Inclusion criteria violated
A2	Exclusion criteria violated
B	Informed consent
B1	Informed consent not available
B2	Informed consent too late
C	Trial medication and randomisation
C1	Incorrect trial medication taken
C3	Non-compliance
C4	Incorrect intake of trial medication
D	Concomitant medication
D1	Prohibited medication use
E	Missing data
	None ¹
G	Other trial specific important violations
G1	Certain violations of procedures used to measure secondary PK data

Violations C1, C2 and G1 can only be detected at the trial site.

¹ Missing visits, evaluations, and tests will be considered missing data, not PVs

Source: BI reference document "Protocol Violation Handling Definitions" (2).

If any IPV, s are identified, they are to be summarised into categories and will be captured in the RPM/DBLM minutes via an accompanying Excel spreadsheet (3). The table above contains the categories which are considered to be IPV, s in this trial. If the data show other IPV, s, this table will be supplemented accordingly by the time of the RPM/DBLM.

IPV, s will be summarised and listed.

6.3 SUBJECT SETS ANALYSED

All entered subjects who received study medication will be included in the safety analysis and in the PK analysis depending on the availability of measurement values, and on their adherence to the CTP.

The following subject sets will be defined for statistical analysis:

- **Treated set (TS):**
This subject set includes all subjects who received at least one dose of study drug. This is the full analysis set population in the sense of ICH-E9. It will be used for analysis of safety, demographic data and baseline characteristics.
- **Pharmacokinetic parameter set (PKS):**
This subject set includes all subjects in the TS who provide at least one primary or secondary PK parameter that was not excluded because of PVs relevant to the statistical evaluation of PK endpoints as defined in Section 7.3 of the CTP.

The discussion of all exceptional cases and problems and the decisions on the allocation of subjects to analysis sets will be made at latest at the RPM/DBLM.

Table 6.3: 1 Subject sets analysed

Class of endpoint	Subject set	
	TS	PKS
Disposition	X	
Exposure	X	
IPVs	X	
Demographic/baseline endpoints	X	
Primary and secondary endpoints		X
Safety parameters	X	

6.5 POOLING OF CENTRES

This section is not applicable, because the study was performed in only one centre.

6.6 HANDLING OF MISSING DATA AND OUTLIERS

CTP: If a subject is removed from or withdraws from the trial prior to first administration of trial medication, the data of this subject will not be entered in the case report form (CRF) or

trial database and will not be reported in the clinical trial report (CTR). If a subject is removed from or withdraws from the trial after first administration of trial medication, this will be documented and the reason for discontinuation must be recorded in the CRF. In this case, the data will be included in the CRF/trial database and will be reported in the CTR.

CTP: *With respect to safety evaluations, it is not planned to impute missing values.*

The only exceptions where imputation might be necessary for safety evaluation are AE dates. Missing or incomplete AE dates are imputed according to BI standards (4).

Missing data and outliers of PK data are handled according to BI standards (5).

Plasma / Urine concentration-time tables

CTP: *Drug concentration data identified with NOS (no sample available), NOR (no valid result), NOA (not analysed), or BLQ (below the lower limit of quantification) will be displayed as such and not replaced by zero at any time point (this rule also applies also to the lag phase, including the predose values).*

Pharmacokinetic parameters

CTP: *Drug concentration data identified with NOS, NOR or NOA will generally not be considered. Concentration values in the lag phase identified as BLQ will be set to zero. All other BLQ values of the profile will be ignored. The lag phase is defined as the period between time zero and the first time point with a concentration above the quantification limit.*

6.7 BASELINE, TIME WINDOWS AND CALCULATED VISITS

For safety measurements baseline is defined as the last measurement before first study drug administration.

Time windows are defined in Section 6.1 of the CTP. Adherence to time windows will be checked at the RPM/DBLM.

7. PLANNED ANALYSIS

The format of the listings and tables will follow the BI guideline "Reporting of clinical trials and project summaries" (6).

The individual values of all subjects will be listed. Listings will generally be sorted by dose group, subject number and visit (if visit is applicable in the respective listing). AE listings will be sorted by assigned treatment (see [Section 7.8.1](#) below for details). The listings will be contained in Appendix 16.2 (SDL) of the CTR.

The following standard descriptive statistical parameters will be displayed in summary tables of continuous variables:

N	number of non-missing observations
Mean	arithmetic mean
SD	standard deviation
Min	minimum
Median	median
Max	maximum

For plasma concentrations as well as for all PK parameters the following descriptive statistics will additionally be calculated:

CV	arithmetic coefficient of variation
gMean	geometric mean
gCV	geometric coefficient of variation

The data format for descriptive statistics of plasma concentrations will be identical with the data format of the respective concentrations. The descriptive statistics of PK parameters will be calculated using the individual values with the number of decimal places as provided by the evaluation program. Then the individual values as well as the descriptive statistics will be reported with three significant digits in the CTR.

Tabulations of frequencies for categorical data will include all possible categories and will display the number of observations in a category as well as the percentage (%) relative to the respective treatment group. Percentages will be rounded to one decimal place. The category missing will be displayed if and only if there actually are missing values. Percentages will be based on all subjects in the respective subject set whether they have non-missing values or not.

7.1 DEMOGRAPHIC AND OTHER BASELINE CHARACTERISTICS

Only descriptive statistics are planned for this section of the CTR. These will be based on the TS.

7.2 CONCOMITANT DISEASES AND MEDICATION

Concomitant diseases will be coded according to the most recent version of MedDRA. Concomitant medication will be coded according to the most recent version of the World Health Organisation – Drug Dictionary.

Only descriptive statistics are planned for this section of the CTR.

A medication will be considered concomitant to a treatment, if it

- is ongoing at the time of administration of the respective treatment or
- starts within the analysis phase of the respective treatment (see [Section 6.1](#) for a definition of treatments and analysis phases).

7.3 TREATMENT COMPLIANCE

Treatment compliance will not be analysed as a specific endpoint. Any deviations from complete intake will be addressed in the RPM/DBLM (cf. [Section 6.2](#)) and described in the CTR.

7.4 PRIMARY ENDPOINTS

Only descriptive statistics are planned for this section of the CTR. These will be based on the PKS. The analysis of standard PK parameters is performed according to BI standards (5) [001-MCS-36-472_RD-01].

Exclusion of PK parameters

The ADS ADPP contains column variables APEXC and APEXCO indicating inclusion/exclusion (APEXC) of a PK parameter and an analysis flag comment (APEXCO). All analyses based on the PKS are based on PK parameter values which are not flagged for exclusion, i.e. with APEXC equal to "Included".

Exclusion of plasma concentrations

The ADS ADPC (PK concentrations per time-point or per time-interval) contains column variables ACEXC or ACEXCO indicating inclusion/exclusion (ACEXC) of a concentration and an analysis flag comment (ACEXCO). Exclusion of a concentration depends on the analysis flag comment ACEXCO. For example, if ACEXCO is set to "ALL CALC", the value will be excluded for all types of analyses based on concentrations. If ACEXCO is set to "DESC STATS" the value will be excluded from descriptive evaluations per planned time point/time interval. If ACEXCO contains the addition "TIME VIOLATION" or "TIME DEVIATION", the value can be used for further analyses based on actual times. If ACEXCO is set to "HALF LIFE", the value will be excluded from half-life calculation only; the value is included for all other analyses. Excluded concentration itself will be listed in the CTR associated with an appropriate flag.

Further details are given in "Noncompartmental Pharmacokinetic / Pharmacodynamic Analyses of Clinical Studies" (5) and "Description of Analytical Transfer Files and PK/PD Data Files" (7).

7.5 SECONDARY ENDPOINTS

7.5.1 Key secondary endpoint

Not applicable.

7.5.2 Secondary endpoints

Only descriptive statistics are planned for this section of the CTR. These will be based on the PKS.

7.6 FURTHER ENDPOINTS

7.6.1 Safety endpoints

Further safety endpoints will be analysed as described in Section 7.8 of this TSAP.

7.7 EXTENT OF EXPOSURE

Only descriptive statistics are planned for this section of the CTR.

7.8 SAFETY ANALYSIS

All safety analyses will be performed on the TS.

7.8.1 Adverse events

AEs will be coded with the most recent version of MedDRA.

The analyses of AEs will be descriptive in nature. All analyses of AEs will be based on the number of subjects with AEs and not on the number of AEs.

For analysis, multiple AE occurrence data on the eCRF will be collapsed into one event provided that all of the following applies:

- All AE attributes are identical (lower level term, intensity, action taken, therapy required, seriousness, reason for seriousness, relationship, outcome, AESI)
- The occurrences were time-overlapping or time-adjacent (time-adjacency of two occurrences is given if the second occurrence started at most 1 hour after the first occurrence ended)

For further details on summarization of AE data, please refer to "Analysis and Presentation of Adverse Event Data from Clinical Trial" (8) [001-MCG-156] and "Handling of missing and incomplete AE dates" (4) [001-MCG-156_RD-01].

The analysis of AEs will be based on the concept of treatment emergent AEs. That means that all AEs will be assigned to the screening phase or on-treatment phase as defined in [Section 6.1](#).

An overall summary of AEs will be presented. This overall summary will comprise summary statistics for the class of other significant AEs according to ICH E3 and for the class of AESIs.

CTP: *The following are considered as AESIs in this trial:*

Hepatic injury

A hepatic injury is defined by the following alterations of hepatic laboratory parameters:

- *an elevation of AST and/or ALT ≥ 3 -fold ULN combined with an elevation of total bilirubin ≥ 2 -fold ULN measured in the same blood sample, and/or*
- *aminotransferase (ALT, and/or AST) elevations ≥ 10 fold ULN.*

The investigator had to classify on the eCRF whether an observed AE was an AESI or not.

According to ICH E3 (9), AEs classified as "other significant" need to be reported and will include those non-serious and non-significant AEs

- (i) which are marked haematological or other lab abnormalities, or
- (ii) which were reported with "action taken = discontinuation" or "action taken = reduced", or
- (iii) which lead to significant concomitant therapy as identified by the Clinical Monitor/Investigator at a Medical Quality Review Meeting.

The frequency of subjects with AEs will be summarised by treatment, primary SOC and preferred term. AEs which were considered by the investigator to be drug related will be summarised separately. Separate tables will also be provided for subjects with SAEs, subjects with AESIs and subjects with other significant AEs (according to ICH E3 (9)). The frequency of subjects with AEs and the frequency of subjects with AEs considered by the investigator to be drug related will also be summarised by maximum CTCAE grade, primary SOC and preferred term.

The SOC and preferred terms within SOC will be sorted by descending frequency overall treatment groups.

For disclosure of AE data on ClinicalTrials.gov, the frequency of subjects with non-serious AEs occurring with an incidence of greater than 5 % (in preferred terms) will be summarised by treatment, primary SOC and preferred term. The frequency of subjects with SAEs will also be summarised.

For disclosure of AE data in the EudraCT register, the frequency of AEs, the frequency of non-serious AEs with an incidence of greater than 5 % (in preferred terms) and the frequency of SAEs will be summarised.

7.8.2 Laboratory data

The analyses of laboratory data will be descriptive in nature and will be based on BI standards "Display and Analysis of Laboratory Data" ([10](#)).

Analyses will be based on normalised values, which means transforming to a standard unit and a standard reference range.

Descriptive statistics of laboratory values over time and for the difference from baseline (see [Section 6.7](#)) will be provided. Frequency tables of changes between baseline and the value two weeks after last study drug intake (i.e., Day 15 for SD group and Day 43 for MD group) with respect to the reference range will be presented.

Possibly clinically significant abnormal laboratory values are only those identified either in the Investigator's comments or at the RPM/DBLM at the latest. It is the Investigator's responsibility to decide whether a lab value is clinically significant abnormal or not. Standard or project-specific rules for flagging clinically significant values in an automated manner will not be applied in this study.

Clinically relevant findings in laboratory data will be reported as baseline conditions (at screening) or as AEs (during the trial) if judged clinically relevant by the investigator, and will be analysed as such.

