#### Drug-related risks and safety measures

##### *On target effects*

BI 1467335 could cause on-target toxicity as its anti-inflammatory effects may reduce the immune response and thus worsen infections. However, a deleterious effect relating to a reduction in leukocyte or lymphocyte migration was not seen in any of the preclinical models. This also true for two completed phase I studies in healthy male and female subjects

Nonetheless, clinical and laboratory signs of reduced immune response will be monitored throughout the study.

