### *Drug-induced liver injury (DILI)*

Although rare, a potential for drug-induced liver injury (DILI) is under constant surveillance by sponsors and regulators. Therefore, this study requires timely detection, evaluation, and follow-up of alterations in selected liver laboratory parameters to ensure subjects' safety.

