### **3.3.4 Removal of subjects from therapy or assessments**

#### **3.3.4.1 Removal of individual subjects**

An individual subject is to be removed from the trial if:

1. The subject withdraws consent for trial treatment or trial participation, without the need to justify the decision
2. The subject needs to take concomitant drugs that interfere with the investigational product or other trial medication
3. The subject is no longer able to participate for other medical reasons (such as surgery, adverse events, or diseases)
4. The subject shows an elevation of AST and/or ALT  $\geq 3$ -fold ULN combined with an elevation of total bilirubin  $\geq 2$ -fold ULN (measured in the same blood sample) and/or needs to be followed up according to the 'DILI checklist' provided in the ISF.
5. A subject can also be removed from the trial if eligibility criteria are being violated or if the subject fails to comply with the protocol (for instance, by non-adherence to dietary rules, or non-attendance at study assessments).

If a subject is removed from or withdraws from the trial prior to first administration of trial medication, the data of this subject will not be entered in the case report form (CRF) or trial database and will not be reported in the clinical trial report (CTR). If a subject is removed from or withdraws from the trial after first administration of trial medication, this will be documented and the reason for discontinuation must be recorded in the CRF. In this case, the data will be included in the CRF/trial database and will be reported in the CTR. At the time of discontinuation a complete end of trial examination will be performed if possible and the information will be recorded in the CRFs. These discontinuations will be discussed in the CTR.

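### In the multiple-dose group, the one reference-range table in SAP 7.8.2 uses Day 43 only, so a transient on-treatment excursion not reported as an adverse event is never counted by subject

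*SAP*

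**What the plan says.** SAP 7.8.2 describes two laboratory summaries.

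- The first is "Descriptive statistics of laboratory values over time and for the difference from baseline". SAP Section 7 defines descriptive statistics for continuous variables as N, mean, SD, minimum, median and maximum.
- The second is "Frequency tables of changes between baseline and the value two weeks after last study drug intake", with the days given as "i.e., Day 15 for SD group and Day 43 for MD group) with respect to the reference range will be presented".

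The same section adds: "Standard or project-specific rules for flagging clinically significant values in an automated manner will not be applied in this study". A laboratory finding becomes an adverse event (AE) only if the investigator judges it clinically relevant. Protocol 7.3.3 has out-of-range values highlighted in the listings.

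Protocol 2.3 names two harms that have laboratory signs. On immune effects it says that "clinical and laboratory signs of reduced immune response will be monitored throughout the study". On drug-induced liver injury it says that "this study requires timely detection, evaluation, and follow-up of alterations in selected liver laboratory parameters".

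**The concern.** The reference-range table is the only place in the SAP text where subjects who move out of range are counted without depending on the investigator's judgement. For MD it looks at one day after dosing has ended, although five full panels are taken while subjects are on drug. A mild ALT rise or a fall in neutrophils or lymphocytes during Days 7 to 35 that recovers by Day 43 would be shown as normal to normal. At stake is whether the report gives a plain subject count for the two kinds of laboratory change that the protocol itself singles out.

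**Working it through.** **Inputs.** Visit days come from the two flow charts and their footnotes, dosing days from Protocol 3.1 and 4.1.4 and SAP 6.1, and the group size of 8 from Protocol 7.6.

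**1. The SAP's own figure (two weeks from last intake to the tabulated value).** Interval = named day minus day of last dose.

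| Group | Last dose | Interval |
|---|---|---|
| SD | Day 1 | 15 − 1 = 14 days |
| MD, as planned | Day 40 | 43 − 40 = 3 days |
| MD, stopped early | Day 35 | 43 − 35 = 8 days |
| MD, stopped early | Day 34 | 43 − 34 = 9 days |
| MD, radiolabelled dose only | Day 28 | 43 − 28 = 15 days |

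The figure reproduces for SD. For MD it would need a last tablet on Day 29 (43 − 29 = 14). Day 28 gives 15 days and is not the last intake when tablets continue. The description and the named day therefore disagree for MD.

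**2. Full safety panels after baseline.** Marks with the haematocrit footnote or the drug-screening footnote are not full panels.

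- MD: Days 7, 14, 21, 28 (predose), 35, 43 and the end-of-trial (EOT) examination = 7. In the table: 1 of 7. During dosing: 5, of which 0 are in the table.
- SD: Day 15 and EOT = 2. In the table: 1 of 2. The marks at 1, 12 and 24 h are haematocrit only, so no full panel lies between the dose and Day 15.

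Under any of the MD intervals in step 1, Days 7 to 35 stay outside the table.

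**3. Size in the MD table.** One subject of 8 = 12.5 percentage points. Illustration with assumed counts: if 1 to 3 of 8 MD subjects have an excursion on Days 7 to 35 that is back in range on Day 43, the table shows 0% where 12.5% to 37.5% had one. This applies to subjects who recover and remain in the trial, not to those removed.

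**4. Where an excursion is counted otherwise.**

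- *Hepatic injury.* An adverse event of special interest (AESI) needs AST/ALT ≥3× ULN with bilirubin ≥2× ULN, or AST/ALT ≥10× ULN. SAP 7.8.1 gives AESIs their own subject table.
- *Discontinuations and marked laboratory abnormalities.* SAP 7.8.1 counts these among other significant AEs, also in a separate table.
- *Any other finding judged relevant.* It is counted as an AE.
- *An isolated rise below 10× ULN, or a white-cell change, not judged relevant.* It enters no subject count.

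**5. Side effect of using all visits.** Assume that 5% of healthy values fall out of range at each visit, independently (not from the documents). The chance of at least one exceedance for one analyte is 1 − 0.95^k.

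- k = 1: 5%, or 0.4 of 8 subjects.
- k = 2 (SD): 1 − 0.9025 = 9.75%.
- k = 7 (MD): 1 − 0.698 = about 30%, or about 2.4 of 8 subjects.

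Positive correlation between a subject's visits would lower the figures for k = 2 and k = 7.

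**The case against.** The strongest reply is that little is hidden. All individual values are listed, out-of-range ones are highlighted, and with 8 subjects per group a reader can count them. Safety is descriptive, and no hypothesis is tested. A worst-value table also collects chance findings, as step 5 shows. This is a fair argument for modest weight and a short analyte list, but listings and by-visit extremes still do not give a subject count.

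Four stronger readings are tempting and are not supported.

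- *Removal for liver toxicity goes uncounted.* Protocol 3.3.4.1 removes a subject when "The subject shows an elevation of AST and/or ALT" at or above threshold occurs together with raised bilirubin. That is also the first AESI criterion, so the subject is counted in the AESI table. The SAP states "With respect to safety evaluations, it is not planned to impute missing values", and Section 7 displays a missing category with percentages based on all subjects. A removed subject without a Day 43 value therefore shows as 1 of 8 missing, not as no shift.
- *SD is affected in the same way.* No SD full panel between dosing and Day 15 is discarded. Only EOT and unscheduled values are left out.
- *The SAP breaks a promise in Protocol 2.3.* Those passages concern monitoring and follow-up during conduct, which the scheduled panels provide. They do not call for a particular table.
- *No other count will exist in the report.* The laboratory analysis also follows a sponsor standard that is not available here, so the statement holds for the SAP text alone.

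**Conclusion.** The point holds for MD values that leave the reference range during dosing, return by Day 43 and are not reported as AEs. For these, the described table shows no shift, and the SAP text offers no subject count. It rests on the flow-chart reading of 7 post-baseline MD panels with 5 during dosing. The documents do not say how often such excursions are expected or how quickly they would resolve, so the 12.5% to 37.5% range is an illustration, not a forecast. Primary and secondary pharmacokinetic results are untouched. This is a low-cost improvement to safety reporting that should be made. The disagreement between the two-week description and Day 43 is a separate inconsistency in the same sentence and also needs resolving.

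**What to change.** In SAP 7.8.2:

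1. Keep the Day 15/Day 43 table.
2. Add a frequency table by group from baseline category to worst post-baseline category, low and high separately. Use all scheduled and unscheduled values from first dose through EOT, for ALT, AST, total bilirubin, white cells, neutrophils and lymphocytes. Subjects removed early contribute the values they have.
3. Footnote the new table. Repeated panels raise chance exceedances (about 30% of subjects per analyte over 7 visits against 5% at one visit, assuming 5% independent exceedance per visit). SD and MD columns should not be compared, because the number of panels differs (2 against 7 scheduled).
4. Reconcile the two-week description with Day 43 for MD.

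The cost is a few lines of SAP text and one table from data already collected. No sample, visit, dose or clinical rule changes.
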